For the purpose of sample size estimation, data from in the Park-Reeves Syringomyelia Research Consortium (PRSRC) were analyzed (ambispective enrollment, n=589 subjects with complete data); specifically, surgical complications ≤ 12 months were used to calculate the sample size. In this dataset, surgical complications were noted in 17.8% of PFDD cases and 2.7% of PFD cases. This is consistent with reported values from a recent meta-analysis, where the rates for CSF-related complications for PFDD and PFD were 18.5% and 1.8%, respectively [27], as well data reported in case series [17, 25] and a systematic review [42]. We expect to observe a similar difference in PFDD versus PFD cases in the proposed study. Because of the clustered randomized nature of the trial, the intraclass correlation coefficient (ICC) should be taken into account. The ICC is defined as the proportion of the between cluster (PRSRC center) variation to the total variation. Since the cluster sizes are small (6 per PRSRC center), and we have a large number of centers available for enrollment (47 total), the effect of ICC on sample size will be small. Thus, using the PRSRC values of 17.8% for PFDD and 2.7% for PFD, and assuming equal number of subjects per group and twosided type I error rate of 0.05, to reach 90% power, 36 centers averaging 6 subjects per center will be required for the trial assuming the ICC is 0.05. To account for 2% dropout rate, we originally planned to recruit 40 centers with a cluster size averaging 6 subjects with overall sample size of enrolled patients of 240 patients, approximately 120 patients per procedure over the two years of enrollment.

Aim 1: Sample Size Recalculation (November 29, 2017)

The original sample size calculation was performed based on surgical complication rates (≤ 12 months) from Park-Reeves Syringomyelia Research Consortium (PRSRC) estimates (17.8% in PFDD and 2.7% in PFD cases). We originally did not have an estimate for the ICC. Based on the literature, we assumed ICC of 0.05 in our calculations [43]. The overall sample size of enrolled patients would be 240 patients, approximately 120 patients per procedure over the two years of enrollment.

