In preparation for our PFD trial annual meeting on November 29, 2017, we performed a sample size re-calculation, using the ICC observed from the 47 patients enrolled in the study and for which complete data was available as of November 28, 2017. It should be noted that the data was only used to calculate the ICC; no interim analyses were performed. The ICC based on the first enrolled 47 patients was 0.000059, much smaller than what was assumed (0.05) for the original sample size calculation. However, we expect this ICC estimate to change with more enrollments.

Enrollment in the trial has increased over time and continues to do so (for example, 10 patients were enrolled in both November and December, 2017 and the total trial enrollment is now 83). However, when calculated at the time of the annual meeting at the end of November 2017, the average accrual rate, calculated over the entire 19-month period of the study, was 6 patients per month. Thus, using the conservative projection of 6 patients per month over the course of an enrollment extension ending 12/1/2018, we expect the total number of subjects to be at least 145 (73 + 12 x 6). (73 was the total enrollment when these calculations were made at the end of November; however, as noted above, 10 patients were recruited in December.)

Based on the enrolled 47 patients in the database with complete data as of 11/28/17, the average cluster size is 2.9. If we assume each center enrolls 3 more patients over the enrollment extension, the average cluster size increases to 5.9. With the current ICC estimate of 0.01 and using the original estimates for the complication rates (17.8% in PFDD and 2.7% in PFD), with the projected sample size of 145, we can still reach 84% power by enrolling patients from 24 centers with an average cluster size of 6 (144 subjects total). The same power level can also be achieved by enrolling patients from 30 centers with an average cluster size of 5. To account for a potential 2% loss to follow up rate, we planned to recruit 148 subjects total (74 per group) over the entire trial enrollment period.

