It should be noted that it is assumed that the average cluster size is 6 in all centers for these calculations. The design effect (DE) concept is used in cluster randomized trials to inflate the sample size of the study, compared to the traditional randomized trials [44]. When cluster size is fixed, $DE = 1 + [(m - 1) \times ICC]$; where m is the average cluster size and ICC is the intraclass correlation coefficient. In other words, the sample size of the study can be calculated by traditional methods, and should be multiplied by the DE. Under the assumption that m = 6 and ICC = 0.01, DE becomes 1.05. To compare 17.8% vs 2.7% surgical complication rates for a (*not clustered*) randomized trial, with 84% power, and 0.05 type I error rate, we would need to enroll 136 patients total. This is also listed in the sample size calculator above under the "unadjusted box". For a DE value of 1.05, this sample size should be multiplied by 1.05 to find the sample size of a cluster randomized trial to reach same power. Therefore, the sample size of the clustered randomized trial would be 136 x 1.05 = 142.8 ~143.

The variable cluster size is common in cluster randomized trials. Eldridge et al considered the effect of variable cluster size on the sample size calculation for cluster randomized trials [45]. They showed that the DE value can be calculated for variable class sizes. DE' = $1 + {(cv^2+1) m - 1} x$ ICC; where cv is the coefficient of variation of cluster sizes (standard deviation of cluster sizes divided by the mean cluster size). The cv is 1.08 for our study. If we use the current average cluster size of m = 2.9, DE' becomes 1.06. In other words, the sample size of the study should be inflated to 136 x 1.06 = 144.16~145 to reach 84% power. This assures us that our planned sample size of 145 patients will allow us to reach 84% power even if our cluster sizes will not be fixed at 6.

It should be noted that, as of March 6th 2018, only 1 of 100 enrolled patients was lost to followup. However, to account for a potential 2% loss to follow up on the 145 subjects needed (72 per group), we will recruit 148 subjects total (74 per group) over the entire trial enrollment period, which is proposed to be extended to December 31, 2018.

Aim 2: Non-Inferiority Margins and Power

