7.5 Data Analyses

A Priori Plans for Data Analysis

Descriptive Statistics

Using CONSORT guidelines for cluster-randomized trials,53 We will present descriptive statistics, for continuous variables the mean (+/-standard deviation) or median (minimum, maximum) values and for categorical variables the frequencies and proportion for each cluster. These presentations will be carried out at baseline and at 12-month follow-up. We will provide reasons for dropouts.

Final Comparative Analysis PCORI CER-1503-29700 Based on Protocol Version 6 March, 2021 *Planned sensitivity analyses to determine the impact of key assumptions.* Due to the fact that each patient in a given center will be assigned to the same procedure, it is possible to observe unequal overall sample sizes for each procedure. The initial analysis plan is to give equal weights to all clusters. If there is imbalance in the prognostic factors, we will use weighted analyses where the cluster-level summary score is weighted inversely proportional to the reciprocal of its estimated variance.

Initial analysis will be conducted using per Treatment group assignment prior to adjudication, as it aligns more to in-practice clinical procedures. Sensitivity analyses will be conducted based upon Intent-to-Treat (ITT) (as randomized), and per Protocol (actual treatment) grouping definitions, both pre and post adjudication. Patients with a second Chiari surgery will be analyzed in two different ways in sensitivity analysis, one including vs one excluding second surgeries. and will be.

Comparison methods

Specific Aim 1: Hypothesis: PFD will be associated with fewer surgical complications and less potential harm to patients than PFDD.

Anticipated Outcome: Cerebrospinal fluid (CSF)-related complications ≤ 6 months (e.g. CSF leak, pseudomeningocele, aseptic meningitis, infection, hydrocephalus), and the requirement for additional surgery for wound revision or CSF diversion will be lower after PFD compared with PFDD.

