The primary outcome is a binomial outcome measured as a surgical complication and/or requirement for reoperation for complication management ≤ 12 (+/- 2 months) months after initial PFDD or PFD. To account for within cluster correlation, possibly variable cluster size and the relatively small number of clusters in this cluster randomized trial, generalized estimating equations (GEE) with small-sample correction or random effect logistic regression will be used for the primary analysis of this cluster randomized trial [35, 36].

Specifically, a GEE model with a logit link function and adjustment for baseline covariates can be expressed as follows:

$logit(\pi_{ij}) = \mu + \delta T_i + x_{ij}\beta$

where $T_i = I$ if group *i* is assigned PFD and 0 otherwise. Accordingly, δ is the intervention effect. Let x_{ij} is the p-dimensional vector of group-level of individual level covariates from individual *j* (*j* = 1, ..., n_i) nested in center *i* (*i* = 1, ..., # of active centers here); and β is the vector of covariate effects. Also let the outcomes (CSF-related complication ≤ 6 months, yes/no) are independently distributed as $y_{ij} \sim \text{Bernoulli}(\pi_{ij})$. Further let, μ be the log-odds of positive outcome ($y_{ij} = 1$) for PFDD subjects with reference values for covariates ($x_{ij} = 0$) and average random effect ($\gamma_i = 0$). The exchangeable correlation structure will be used for the within-group homogeneity for the correlation structure of the outcomes. Note that, this correlation parameter corresponds to the intraclass correlation coefficient (ICC).

Specific Aim 2:

Hypothesis: Clinical improvement and syrinx regression provided by PFD will be non-inferior compared to those provided by PFDD.

Anticipated Outcome: Clinical symptoms, neurological function, and syrinx regression ≤ 12 months (± 2 months) provided by PFD will be non-inferior compared to those provided by PFDD. The non-inferiority margin is defined as the difference between the outcome rates by treatment. For the clinical improvement outcome, a non-inferiority margin of 0.17 units will be used. A non-inferiority margin of 0.135 units will be used for the syrinx regression outcome.

Clinical symptoms, neurological function, and syrinx regression are defined as rates of change from baseline to 12 months. The 1-sided confidence interval for the difference in rates between the PFD and PFDD groups will be calculated and compared to the corresponding non-inferiority margins.

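### The plan makes equal centre weights the initial rule but names a model that weights nearly by patient as primary, and does not say which decides Aim 1; the stated 84% power holds only for the latter.

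*SAP*

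**What the plan says.** **Weighting rule.** SAP 7.5, Final Comparative Analysis, states: "The initial analysis plan is to give equal weights to all clusters". Protocol 9.5 has the same sentence. In both documents the paragraph opens with a sub-heading on planned sensitivity analyses. It leaves equal weighting only if prognostic factors are imbalanced. Variation in centre size is not a trigger.

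**Primary analysis.** Under Specific Aim 1, SAP 7.5 says that GEE with small-sample correction or random-effect logistic regression "will be used for the primary analysis of this cluster randomized trial", and gives possibly variable cluster size as one reason. Protocol 9.5, Comparison methods, names the same two models. The SAP adds a logit link and an exchangeable working correlation.

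**Sample size.** SAP 7.2 counts patients and inflates for clustering: "Under the assumption that m = 6 and ICC = 0.01, DE becomes 1.05". It then allows for unequal centres: "The cv is 1.08 for our study". It gives no power for an analysis that weights centres equally.

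**The concern.** Both weighting statements stand under Final Comparative Analysis, and nothing connects them. Two statisticians could follow the same SAP and report different Aim 1 estimates, one averaging centre proportions and one fitting the GEE. A choice left open at this point could be made after the data are seen.

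The two rules differ most when centre sizes vary widely and the ICC is near zero, which is what the SAP reports: "The ICC based on the first enrolled 47 patients was 0.000059". With 12 centres per arm (the SAP's 24-centre scenario), one complication in a one-patient centre moves an equal-weight arm rate by 1/12 = 8.3 percentage points. Counted by patient, with about 72.5 per arm, it moves the rate by 1/72.5 = 1.4 points. The planned difference is 17.8 - 2.7 = 15.1 points.

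**Working it through.** **Inputs**

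- Complication rates (SAP 7.2): "using the PRSRC values of 17.8% for PFDD and 2.7% for PFD"
- Allocation and alpha (SAP 7.2): "assuming equal number of subjects per group and twosided type I error rate of 0.05"
- ICC 0.01 for planning, 0.000059 observed in the first 47 patients (SAP 7.2)
- cv 1.08; mean centre size 2.9 in the November 2017 data, 5 or 6 in the planning scenarios (SAP 7.2)
- 145 patients needed, 148 to recruit (SAP 7.2)
- Centre-size distribution: not in the documents, so assumed

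**Step 1. Reproduce the plan.** With n per arm and p̄ = (0.178 + 0.027)/2 = 0.1025,

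power = Φ{ [0.151√n - 1.96√(2p̄(1-p̄))] / √(0.178×0.822 + 0.027×0.973) }.

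- At n = 68 this is 83.5%. Solving for 84% gives 138 in total, against the SAP's 136.
- Fixed centre size: 136 × 1.05 = 142.8.
- Unequal sizes: DE' = 1 + {(1.08² + 1) × 2.9 - 1} × 0.01 = 1.053. The SAP has 1.06, which gives 136 × 1.06 = 144.2, hence 145.
- Power at 145 patients with DE' 1.053: 84.0%. With mean size 6 and cv 1.08, DE' = 1.120 and power is 81.6%. With ICC 0 it is 85.8%.

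The plan's figure therefore reproduces for an analysis that weights by patient: 82-86% by formula.

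**Step 2. What the GEE weights.** Under an exchangeable correlation a centre of n patients gets weight n / {1 + (n-1) × ICC}.

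| Patients in centre | 1 | 3 | 6 | 15 |
|---|---|---|---|---|
| Equal weights | 1 | 1 | 1 | 1 |
| GEE, ICC 0.01 | 1 | 2.9 | 5.7 | 13.2 |

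At ICC 0.000059 the GEE weights are, to one decimal, the patient counts themselves.

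**Step 3. Cost of equal weights.** Relative to an unclustered analysis of the same patients, averaging k centre proportions equally inflates the variance by

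VIF = mean(n) × mean[ {1 + (n-1) × ICC} / n ],

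which at ICC 0 is mean(n) × mean(1/n). Power is then taken at 145/VIF patients.

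Two constructed examples have 16 centres and 47 patients, matching the SAP's mean of 2.9 (ICC 0):

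- Skewed: eight centres of 1, three of 2, and one each of 3, 4, 6, 9 and 11. The cv is 1.06 and mean(1/n) is 0.653, so VIF = 2.94 × 0.653 = 1.92. Effective patients are 145/1.92 = 75.5 and power is 58%.
- One large centre: thirteen of 2, two of 3, one of 15. The cv is 1.10 and mean(1/n) is 0.452, so VIF = 2.94 × 0.452 = 1.33. Effective patients are 109 and power is 75%.

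Across negative binomial and rounded lognormal sizes with cv 1.08 and means from 2.9 to 6, VIF runs from about 1.7 (power 64%) to 2.5 (power 47%).

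**Step 4. Simulation check.** 3,000 trials per scenario used beta-binomial outcomes and rounded lognormal or gamma centre sizes with cv near 1.08. An equal-weight Welch t-test on centre proportions was compared with a patient-weighted ratio estimator (cluster-robust variance, t with centres minus 2 degrees of freedom). The latter stands in for the GEE. The rows below are for ICC 0.01.

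| Centres, patients | Sizes | Equal weights | Patient-weighted |
|---|---|---|---|
| 24, 145 | lognormal | 57% | 83% |
| 24, 145 | gamma | 49% | 85% |
| 30, 148 | lognormal | 62% | 86% |
| 30, 148 | gamma | 55% | 85% |
| 43, 148 | lognormal | 67% | 87% |
| 43, 148 | gamma | 63% | 87% |

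Over all scenarios run, including ICC 0, equal weights gave 49-67% and patient weighting 83-88%.

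**The case against.** The strongest reply is that the plan already settles the matter. Only one analysis is called primary, it is the GEE or random-effect model, and it was chosen with variable cluster size in mind. The equal-weight sentence falls under a sensitivity sub-heading, and a sensitivity analysis may weight differently without contradicting anything. Both documents also call centres the unit of inference, so a centre-average effect is a legitimate target.

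Much of this stands. A reader might infer that equal weighting is the primary analysis and that the trial therefore has little more than even power. The documents do not support that. The inference leans on the next SAP paragraph, which sets an initial analysis against sensitivity analyses, but that paragraph concerns treatment grouping and adjudication and is absent from the protocol. Nor is the 84% wrong: it belongs to the analysis named as primary.

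What the reply does not remove is the gap. Within its own paragraph, equal weighting is the starting rule and weighting is the conditional departure, so the sub-heading alone does not show that the paragraph describes a side analysis. Calling centres the unit of inference makes a centre-level reading more natural. No sentence ties the paragraph to the model that follows.

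**Conclusion.** The concern holds as an unresolved statement of which weighting decides Aim 1. It does not show that the trial is underpowered. Under the named primary model, power is about 82-87% at ICC 0 to 0.01, in line with the stated 84%. Only if the equal-weight result were taken as decisive would power fall to roughly 50-65%.

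That range rests on three assumptions: typically skewed centre sizes, which the documents do not report; the cv of 1.08, reported alongside the November 2017 data (47 patients), persisting to the end of enrolment; and the planning rates of 17.8% and 2.7%. If one large centre produced the cv, the figure would be about 75%. A reader should not take any narrower range as established.

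A second fault in the same paragraph needs no assumption. The fallback weighting inverts a reciprocal, so read literally it gives the least precise centres the most weight.

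**What to change.** In SAP 7.5 and Protocol 9.5, replace the equal-weight sentence with:

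> The primary Aim 1 analysis is the patient-level model named under Specific Aim 1, with clusters weighted as that model implies; an analysis giving each centre equal weight is a sensitivity analysis.

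In Protocol 9.5 the cross-reference should point to Comparison methods, where the model is named. In the next sentence of both documents, change the fallback so that each cluster-level summary is weighted by the reciprocal of its estimated variance.

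The cost is two sentences in each document. No data collection or sample size changes, and the equal-weight result is still reported. The change should be dated before the Aim 1 comparison is run.

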#### **Final Comparative Analysis**

*Planned sensitivity analyses to determine the impact of key assumptions:* Due to the fact that each patient in a given center will be assigned to the same procedure, it is possible to observe unequal overall sample sizes for each procedure. The initial analysis plan is to give equal weights to all clusters. If there is imbalance in the prognostic factors, we will use weighted analyses where the cluster-level summary score is weighted inversely proportional to the reciprocal of its estimated variance.

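### The weighting rule triggered by prognostic imbalance cannot correct imbalance, and as worded it gives the noisiest centres the most weight

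*SAP*

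**What the plan says.** The rule is in SAP 7.5 and Protocol 9.5, both times under Final Comparative Analysis. The paragraph opens "Planned sensitivity analyses to determine the impact of key assumptions" and notes that the arms may end up unequal in size because whole centres are allocated. It continues: "The initial analysis plan is to give equal weights to all clusters". The trigger and the response follow: if prognostic factors are imbalanced, "we will use weighted analyses where the cluster-level summary score is weighted inversely proportional to the reciprocal of its estimated variance". The wording is the same in both documents. Neither lists the prognostic factors, sets a threshold for imbalance, or says how a centre's variance is to be estimated.

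The primary Aim 1 analysis is specified separately, under Comparison methods: "generalized estimating equations (GEE) with small-sample correction or random effect logistic regression will be used for the primary analysis". The SAP then writes out "a GEE model with a logit link function and adjustment for baseline covariates can be expressed as follows". The covariates in that vector are not named.

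**The concern.** Imbalance is a real prospect. Centres know their arm before recruiting, and families know it when they consent (Protocol 5.1 and 6.2.2). Patients for whom the allocated procedure is judged unsuitable are not enrolled (Protocol 4.3 and 5.1). A prespecified response to imbalance therefore matters, and this one has three faults.

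- **It does not address imbalance.** A variance weight depends on centre size and, for a proportion, on the centre's event rate. It carries no information on age, syrinx diameter, tonsillar ectopia or comorbidity.
- **The direction is inverted.** Inversely proportional to 1/variance means proportional to variance.
- **It handles small centres with rare events badly.** A centre's own binomial variance is zero when it has no events. Literal weights are then zero and ordinary inverse-variance weights are infinite.

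At stake is a check that would be reported as dealing with imbalance when it does not, and that could shift the complication difference for reasons unrelated to case mix.

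**Working it through.** **Inputs.** Complication rates 17.8% (PFDD) and 2.7% (PFD), a difference of 15.1 points; 72 evaluable patients per arm; 24 centres of 6, taken as 12 per arm; mean centre size 2.9 at the 2017 recalculation; ICC 0.01; cluster-size cv 1.08. All are from SAP 7.2 except the even split of centres.

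**The plan's own figure.** The documents give no number for the weighted analysis. The unclustered sample size can be checked: the pooled two-proportion formula at two-sided 0.05 and 84% power gives 69 per arm, or 138 in total, against 136 stated. That is within 2 patients, so the inputs are being read as the plan uses them.

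**Step 1: literal direction.** Weight ∝ 1/(1/variance) = variance.

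**Step 2: event-free centres.** P(no events) = (1-p)^m.

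| Patients per centre | PFDD | PFD |
|---|---|---|
| 6 | 0.822^6 = 30.8% | 0.973^6 = 84.9% |
| 3 | 0.822^3 = 55.5% | 0.973^3 = 92.1% |

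At 6 per centre, about 10 of 12 PFD centres and 4 of 12 PFDD centres have an own-centre variance of zero.

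**Step 3: weighted rate, literal rule.** Assume variance p̂(1-p̂)/m, equal sizes and no ICC. The large-sample weighted rate is E[p̂²(1-p̂)] / E[p̂(1-p̂)] = [1+(m-2)p]/m. Any difference between arms is therefore multiplied by (m-2)/m.

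| m | PFDD | PFD | Difference |
|---|---|---|---|
| true | 17.8% | 2.7% | 15.1 points |
| 6 | (1+4×0.178)/6 = 28.5% | (1+4×0.027)/6 = 18.5% | 10.1 points |
| 3 | (1+0.178)/3 = 39.3% | (1+0.027)/3 = 34.2% | 5.0 points |

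**Step 4: trial-to-trial behaviour.** Simulation of 24 centres of 6 under the same literal rule:

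| ICC | Mean difference | Zero or reversed, where estimable | Not estimable |
|---|---|---|---|
| 0 | 10.1 points | 6.8% | 13.9% |
| 0.01 | 10.1 points | 8.4% | 14.6% |
| 0.05 | 9.8 points | 13.5% | 17.2% |

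With equal weights the difference is zero or reversed in at most 0.25% of these trials. With an assumed layout of variable sizes (42 centres, mean about 3.4, cv about 1.08, ICC 0.01), the mean difference is 12.8 points, 21% of estimable trials are zero or reversed, and 19% are not estimable.

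**Step 5: dependence on the estimator.** Adding 0.5 to events and non-events at 6 per centre, the literal rule gives 24.0% vs 5.8%, or 18.2 points, which is larger than the truth. Inverse-variance weights with the same correction give 10.5% vs 1.1%, or 9.4 points. With a variance pooled within arm, p(1-p)/n, the literal weight is proportional to 1/n: equal-sized centres keep equal weight and there is no distortion, but a 1-patient centre counts ten times a 10-patient centre.

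**Step 6: does weighting remove imbalance?** Assume no treatment effect and a risk factor present in 60% of PFDD and 30% of PFD patients, with complication risk 25% with it and 5% without. The crude rates are 0.6×25 + 0.4×5 = 17% and 0.3×25 + 0.7×5 = 11%, a false difference of 6 points. Simulated results:

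| Analysis | False difference |
|---|---|
| Equal weights | 6.00 points |
| Rule as worded | 4.13 points |
| Inverse variance, 0.5 added | 4.55 points |
| Stratified on the factor | 0.05 points |

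The fall to 4.13 is not bias correction. It is close to the (m-2)/m shrinkage of Step 3 (6 × 4/6 = 4.0), which reduces real effects in the same proportion.

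**The case against.** **It is a sensitivity analysis.** This largely stands. The primary analysis is GEE or random-effect logistic regression, and the weighting does not change that estimate. The status could be clearer, because the paragraph sits under Final Comparative Analysis and calls equal weighting the initial plan.

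**The plan already adjusts for covariates.** This also stands. A reader might infer that weighting is the plan's only answer to case mix. It is not, since the SAP's Aim 1 model has a baseline covariate vector. That vector is unnamed, however, and the weighting rule is the only response tied explicitly to imbalance.

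**The wording is probably a slip for inverse variance.** That is plausible, although it appears in both documents. Correcting the slip still leaves a precision weight in the place of an imbalance correction, and own-centre variances still fail in event-free centres.

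**Zero weights come from an assumed estimator.** Correct. Neither document specifies own-centre p(1-p)/m, and a pooled variance would not produce zero weights. The figures in Steps 2 to 4 are conditional on that choice.

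**Trials with no PFD events are not a special fault of weighting.** Correct. The chance of none in 72 patients is 0.973^72 = 13.9%, and in those trials the logit GEE treatment effect is not finite either.

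**Screening logs are reviewed for biased enrolment** (Protocol 4.3, 4.4 and 6.2.1). This may limit imbalance, and its likelihood is not quantified here. It does not make the stated response suitable if imbalance occurs.

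**Conclusion.** The rule is wrong as written in both documents. It inverts the weight, and variance weighting in either direction does not correct prognostic imbalance. This rests on the wording and needs no assumed figures.

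The size is illustrative. With own-centre binomial variances, equal centre sizes and no ICC, the 15.1-point difference shrinks on average to about 10 points (6 per centre) or 5 points (3 per centre). In the simulations with 6 per centre it is zero or reversed in about 7% to 14% of estimable trials as the ICC goes from 0 to 0.05. Other estimators give different distortions, or none when a pooled variance meets equal centre sizes.

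A reader might infer that the rule typically wipes out PFD's complication advantage, or that it puts the primary result at risk. The documents support neither: on average the advantage persists under the worst-case reading, and the rule belongs to the sensitivity analyses. The supportable concern is a check that leaves imbalance uncorrected and could be misread as having dealt with it. It should be corrected.

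**What to change.** 1. **Delete the imbalance-triggered weighting sentence** in SAP 7.5 and Protocol 9.5. Alternatively, restate it purely as a precision sensitivity analysis, with true inverse-variance weights and no imbalance trigger. Name a variance estimator that handles event-free centres. One pooled within arm or model-based is preferable, since Step 5 shows that adding 0.5 to each centre's counts still distorts the rates. The equal-weight cluster analysis can stay.
2. **Name the covariates in the SAP's Aim 1 model** and adjust for them whether or not imbalance is seen. Candidates that the plan already uses for subgroups and imputation are age, syrinx diameter, tonsillar ectopia and preoperative hydrocephalus or neuromuscular disease.
3. **For Aim 1, fix one or two covariates before outcome data are seen**, not by observed event count. Consider the two comorbidities first: the SAP's heterogeneity section links them to morbidity after this surgery, whereas Protocol 7.2.1 links syrinx size to clinical outcome.

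**Cost.** Wording changes in two documents and no new data. The limitation is events: 72×0.178 + 72×0.027 = 12.8 + 1.9, or about 15 expected, so Aim 1 can carry few covariates and some imbalance may remain unadjusted. The change does not solve the case of no PFD events, which needs its own provision.
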